### 2.1.3 Efficacy endpoints

An independent Clinical Endpoint Committee (CEC) will review and adjudicate all events of death and selected CV events (MIs, strokes, unstable angina requiring hospitalization, hospitalization for heart failure (HHF), and coronary revascularization) in a blinded manner. Only events positively adjudicated by the CEC will be included for main efficacy analysis, unless otherwise specified.

All randomized patients (irrespective of whether they experienced efficacy event[s] or whether they permanently discontinued double-blind treatment) will be followed from randomization until the planned last study visit (follow-up visit or study closeout visit for patient premature discontinued IMP). All events occurring on or after randomization and up to patient's end of study date will be included, unless otherwise specified below.

For positively adjudicated efficacy endpoint events with onset date after the patient's end of study date:

1. For patients who prematurely discontinued study, these events will be included in efficacy analysis if the events occur on or before the scheduled study-close out visit. Otherwise, these events will be listed as applicable and not be included in primary efficacy analysis
2. For study completers, these events will be included in efficacy analysis if the proceeding/related event onset date is on or before the patient's scheduled last study visit. Otherwise, these events will be listed separately as applicable and not be included in primary efficacy analysis

For example, for a CV death, if the onset date of its preceding fatal stroke is before the patient's follow-up visit and the CV death date is after follow-up visit (before data base lock (DBL) date), this CV death will be included in efficacy analysis if adjudicated as cardiovascular death.

Any endpoint events reported in the database, but not listed above, will not be included in the efficacy analysis.

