##### **2.3.4.1.2 Censoring rule**

Patients will be right-censored at the last date with information available on the CV outcomes if they have not experienced any positively-adjudicated component of the primary composite CV events on or before their end of study visit. Specifically, the censoring date is defined as follows:

- Patients who completed the study will be censored at their scheduled last study visit date (study close-out visit date or final follow-up visit date)
- Patients who died before completing or discontinuing the study (ie, death reported on the Completion of End of Study form) will be censored at their date of non-CV death

- Patients who discontinued the study will be censored at their later of study discontinuation date or latest date with cardiovascular efficacy endpoint information (MI/UA, heart failure, cerebrovascular event, admission to hospital/emergency room, coronary procedure, or cardiac biomarkers as collected in eCRF) collected. For more details of censoring rule, please refer to [Appendix C](#).

Kaplan-Meier curves of the cumulative incidence rate will be provided by treatment groups over on-study efficacy period (from randomization to end of study date). The incidence rate per 100 patient-years (calculated by 100 \* number of patients with events / sum of time at risk (days) over all patients/365.25) will be reported. For patients with an event, patient-year is time from randomization to first event; for patient without any event, patient-year is from randomization to censoring date.

Underlying assumptions of the Cox proportional hazards model will be checked by visual inspection of the Kaplan-Meier plots (log(-log(survival)) vs log(survival time)).

Individual components of the primary endpoints will be analyzed using the same Cox proportional hazards model described above. Censoring rules described above will be used, and for components other than CV death, patients who died before completing or discontinuing the study will be censored at date of death (i.e. CV or non-CV death). See [Appendix C](#) for specific censoring rules.

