#### Assessment of missing data

For patients who discontinued study but no MACE event was positively adjudicated by scheduled study closeout visit, the missing data are events that may occur after a patient is censored (the later of the patient's study discontinuation date and the last date they have information on CV efficacy endpoint for patients who discontinued the study).

[figure not shown]
Reasons for censoring (including non-CV death, completed study, and study discontinuation reasons) will be summarized. For patients who discontinued the study, the time from censoring date to planned study close-out visit date will be summarized to show the magnitude of missing information.

Subjects prematurely and permanently discontinuing IMP, for other reason than death, prior to study end could have a different event and hazard rate from those who stay on IMP throughout the study, and their corresponding dropout could be considered informative. This subgroup can be divided into subjects with information and subjects with missing information regarding primary MACE endpoints, see figure below.

Diagram showing subjects divided into subgroups related to missing information about MACE.

Subjects with information related to the MACE endpoint events (either discontinued study but have MACE prior to scheduled study closeout visit, or completed the study) will be used to impute data in subjects without MACE endpoints (discontinued study and no MACE event reported through third party data by scheduled study closeout visit). Subjects who developed MACE prior to the IMP discontinuation are included for imputation and their time to MACE data will be used for the imputation modeling. With these subjects included, the model estimate of hazard should fully reflect the potential hazard of the subjects with missing outcome. More specifically, subjects from below scenarios 2 and 3 will be used to impute the missing data of scenario 4 of the same treatment arm:

Note:

1. SCV: study close-out visit;
2. MACE censoring date of scenario 4 is the later of study discontinuation date or latest date with CV event information collected

The following supportive analyses will be performed to evaluate how the primary efficacy results could be influenced by different assumptions about the missing data. In particular, a 4-step approach will be used:

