### ***Censoring***

The underlying rule for censoring is that the censoring date should be the last date the patient is known to be free of the event endpoint (free of each component for composite endpoint) on or before study close-out visit.

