#### ***a. General censoring rule for primary MACE efficacy endpoint:***

For patients who have no primary MACE endpoints, they will be censored using the following rules:

- Patients who completed the study and not died before the study completion will be censored at their study close-out visit date or follow-up visit date.

Note: If there are CV events happening after the patient's study close-out visit date and the event's proceeding/related event's onset date is on or before the study close-out visit date, in this case, this CV events will be included in efficacy analysis if it positively adjudicated. The patient will still be censored at study close-out visit date if these events not adjudicated positively.

For example, for a CV death, if the onset date of its proceeding fatal stoke is before the patient's study close-out visit date and the CV death date is after study close-out visit date (before DBL date), this CV death will be included in efficacy analysis if positively adjudicated as CV death.

Another example, for a HHF, if the onset date of its proceeding HF is before study close-out visit date and its resulted hospitalization is after study close-out visit date, this HHF will be included in efficacy analysis if positively adjudicated. Otherwise, the patient will be censored at study close-out visit date if the HHF is not positively adjudicated.

- Patients who died before study close-out (i.e. Death reported on the 'Completion of End of Study') will be censored at their date of Non-CV death
- Patients who discontinued the study will be censored at their later of study discontinuation date or latest date with cardiovascular efficacy endpoint information (MI/UA, heart failure,

cerebrovascular event, coronary procedure, admission to hospital/emergency room, or cardiac biomarkers as collected in eCRF) collected.

More specific: If there are events happening after the patient's study discontinuation date and the events are not positively adjudicated, the latest date of these events will be the new censored date of the patient.

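### For patients who leave the study, the SAP counts MACE up to close-out, but its censoring bullets, read literally, give no event-free time for a MACE-free final contact

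*SAP*

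**What the plan says.** **Events.** SAP 2.1.3 (item 1) deals with positively adjudicated events after a patient has left the study: "these events will be included in efficacy analysis if the events occur on or before the scheduled study-close out visit". SAP 2.1 (Completion of Study, item 3) requires sites to make a final contact with leavers for outcome collection or, failing that, for vital status, where this is allowed.

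**Censoring, narrow wording.** SAP 2.3.4.1.2 and Appendix C rule a say: "Patients who discontinued the study will be censored at their later of study discontinuation date or latest date with cardiovascular efficacy endpoint information". A parenthesis lists what that information is: MI or unstable angina, heart failure, cerebrovascular events, admissions, coronary procedures and cardiac biomarkers recorded in the eCRF. Appendix C adds that for later events not positively adjudicated, "the latest date of these events will be the new censored date of the patient". Note 2 in the missing-data section also refers to events: "MACE censoring date of scenario 4 is the later of study discontinuation date or latest date with CV event information collected".

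**Censoring, broad wording.** The lead sentence of 2.3.4.1.2 reads "Patients will be right-censored at the last date with information available on the CV outcomes". Appendix C opens its censoring section with the principle that "the censoring date should be the last date the patient is known to be free of the event endpoint". The first paragraph of the missing-data section uses "the last date they have information on CV efficacy endpoint for patients who discontinued the study".

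**Person-time.** Incidence rates use the same date: "for patient without any event, patient-year is from randomization to censoring date".

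**The concern.** Take two leavers reached at the final contact. One had an adjudicated stroke after leaving, and it is counted. The other had no MACE and nothing else to report. Under the narrow wording the second patient is censored at discontinuation, and under the broad wording at the contact. If the narrow wording is programmed, follow-up after leaving depends partly on outcome: events enter the numerator, but the matching event-free time stays out of the denominator.

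Three things are affected: the arm rates per 100 patient-years, the risk sets of the primary Cox model, and the multiple imputation in Appendix D, which starts from the censoring date. No planned analysis isolates the choice. The tipping-point analysis inherits whichever date was derived, and the on-treatment analysis stops 30 days after the last dose.

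**Working it through.** **Inputs (SAP 1.3).** 4000 participants at 1:1:1, so 1333 placebo and 2667 pooled active; 2% per year leaving; follow-up 24 to 36 months; placebo MACE 4.4% per year without and 3.7% with an SGLT2 inhibitor; 15% risk reduction without and none with; SGLT2 use 20% plus 10% (placebo) or 5% (active).

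**Assumptions.** Constant hazards, uniform accrual, add-on SGLT2 use present throughout, contact made at close-out, non-CV death ignored. The last two overstate the event-free time.

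**Blended rates.** Placebo 0.70 × 4.4 + 0.30 × 3.7 = 4.19 per 100 patient-years. Active 0.75 × 0.85 × 4.4 + 0.25 × 3.7 = 3.73. HR = 3.73 / 4.19 = 0.890.

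**The plan's own figure.** With 330 events, SE(log HR) = √(1/110 + 1/220) = 0.117. Power = Φ((ln 1.3 − ln 0.890)/0.117 − 1.96) = 0.900. The stated 90% reproduces.

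**Two readings, all leavers ascertained.** With MACE rate λ, leaving rate δ and time to close-out T, on-study patient-years are N × mean of (1 − e^−(λ+δ)T)/(λ+δ). Leavers = δ × on-study years, and late MACE = λ × years after leaving.

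| | Placebo | Active |
|---|---|---|
| On-study patient-years | 3085 | 6206 |
| Leavers | 61.7 | 124.1 |
| Years after leaving, to MACE or close-out | 77.3 | 155.9 |
| of which in patients with late MACE | 2.8 | 4.9 |
| Late MACE | 3.2 | 5.8 |

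Both readings count the 9 late MACE. The literal bullets omit (77.3 − 2.8) + (155.9 − 4.9) = about 225 event-free patient-years.

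Rate inflation:
- placebo (3085 + 77.3)/(3085 + 2.8) = 1.024, that is, 4.29 instead of 4.19;
- active (6206 + 155.9)/(6206 + 4.9) = 1.024.

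The ratio of the two is 1.000, so the HR does not move.

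**Other ascertainment shares.** None of these is a document figure. The lower end of each range assumes that half of the MACE-free leavers have a listed CV record after leaving.

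| Leavers ascertained | Late MACE | Patient-years omitted | Rates |
|---|---|---|---|
| 0% | 0 | 0 | no change |
| 25% | about 2 | 42 to 56 | +0.5 to 0.6% |
| 50% | about 5 | 84 to 113 | +0.9 to 1.2% |
| 100% | about 9 | 169 to 225 | +1.8 to 2.4% |

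The planning inputs run for 24 to 36 months give about 370 events. Shortened to stop at 330 (about 1.72 to 2.72 years), the maximum is about 166 leavers, 7 late MACE, 181 patient-years and +2.2%.

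**When the HR moves.** Ratio of HR under the literal reading to HR under the broad reading, full ascertainment, leaving rates assumed (placebo/active per year): 2%/3% 1.012; 1.5%/3% 1.018; 2%/4% 1.024; 1%/4% 1.036. In the other direction: 3%/1.5% 0.983; 4%/2% 0.977; 4%/1% 0.965. Equal leaving with 50% against 75% ascertained gives 1.006, and reversed 0.994. A large simulation with a Cox fit agrees: 0.9999 for equal leaving and 1.0185 for 1.5%/3%.

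**Appendix D.** The code draws the imputed time conditional on survival to the censoring date. If that date is discontinuation for a patient known to be MACE-free until the contact, MACE can be imputed inside the known event-free interval.

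**The case against.** The best defence is that the Appendix C principle heads the section and governs the rules beneath it. The parenthesis may list eCRF pages to consult rather than positive findings, and a dated negative answer at a contact made for outcome collection is plausibly endpoint information. The documents do not show whether the eCRF records such an answer.

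This is a fair reading, and it may be the intended one. But it does not remove the conflict. Note 2 refers to event information, and the all-cause mortality rule in Appendix C names the date last known alive. So the SAP specifies an event-free date when it means to use one, and the MACE bullets have no equivalent.

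It also stands that SAP 2.2 and the missing-data section already report study discontinuation by arm, endpoint status before leaving, vital status at planned close-out, censoring reasons, and time from censoring to close-out. Only part of the reporting is missing.

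Three stronger inferences are tempting, and the documents do not support them:
- *The comparison is biased or loses power.* Any HR shift needs an assumed imbalance between arms in leaving or ascertainment. No document figure supplies one, and the direction could go either way.
- *The event-counting rule is wrong.* It is sound. The defect is in the censoring text.
- *The protocol already settles it.* Protocol Table 7 censors at the last available CV information, but no later than the participant's study end date. The SAP's definition of that date for non-completers would place the cap at discontinuation.

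**Conclusion.** The point holds as a minor internal inconsistency in SAP 2.3.4.1.2, Appendix C rule a and note 2 of the missing-data section. Followed literally, these make follow-up after leaving depend on outcome and contradict the SAP's own underlying rule.

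Arm rates would be inflated by 0 to about 2.4%, or at most about 2.2% on a 330-event basis. The upper figures need every leaver ascertained, which is unlikely because outcome collection is conditional on what patients allow.

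The HR is unchanged when leaving and ascertainment are equal by arm. It moves by about 1 to 4%, in either direction, only under assumed imbalance in leaving with high ascertainment. The non-inferiority conclusion is not expected to change, and no power loss should be claimed.

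The possible imputation of MACE into known event-free time is a further reason to settle the wording. Whether the literal reading would be programmed cannot be known from the documents.

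**What to change.** 1. State in SAP 2.3.4.1.2 and Appendix C rule a that a dated contact or third-party source establishing MACE-free status counts as CV endpoint information, with censoring at that date, capped at the scheduled close-out visit. A contact giving vital status only does not count.
2. Use the same date as the scenario 4 censoring date in note 2 and in Appendix D.
3. Keep all positively adjudicated MACE in the primary analysis.
4. Add to the existing disposition and missing-data summaries, by arm, the number of leavers with MACE status ascertained after leaving and the number of late MACE.
5. Optionally, add one supportive analysis that censors all leavers at discontinuation and excludes later events. It departs from the ITT follow-up, so it should be labelled supportive. It would also show any remaining outcome dependence from CV deaths found through vital-status checks.

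The cost is one sentence in two places, an aligned note, one derived date and a few table rows. If the eCRF has no dated MACE-free field, sites must record that date at the final contact they already have to make. This could be a late change, because the SAP refers to pooled data already observed. If it is not feasible, only the counts and the supportive analysis remain.

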#### **2.1.3.1 Primary efficacy endpoint(s)**

The primary efficacy endpoint is:

- Time to the first occurrence of any of the following 3-point MACE events:
  - CV death
  - Non-fatal MI
  - Non-fatal stroke

The death events adjudicated by CEC as ‘undetermined death’ will be considered as CV death and included in efficacy analysis.

#### **2.1.3.2 Secondary efficacy endpoint(s)**

- Time to first occurrence of non-fatal stroke and death
- Time to the first occurrence of any of the following expanded CV events:
  - CV death
  - Non-fatal MI
  - Non-fatal stroke
  - Coronary revascularization
  - Hospitalization for unstable angina
- Time to the first occurrence of any of the following new or worsening nephropathy:
  - New onset or progression to macro albuminuria ( $>300$  mg/g) accompanied by an UACR value increase of  $\geq 30\%$  from Baseline
  - Sustained  $\geq 40\%$  decrease in eGFR from Baseline (for  $\geq 30$  days)
  - Chronic dialysis (for  $\geq 90$  days)
  - Renal transplant
  - Sustained eGFR  $<15$  mL/min/1.73 m^2 (for  $\geq 30$  days)

Low eGFR value and 40% eGFR decrease from baseline will be captured from dedicated eGFR page “Renal event-eGFR Decrease”. Participants with a suspected renal event (reduction of eGFR) should have a repeat assessment of renal function 30 to 45 days following the onset of the event to confirm it is sustained. For UACR increase, it will be captured and reported by lab. Chronic dialysis and renal transplant will be recorded in eCRF procedure pages: “Renal Event – Dialysis Procedure” and/or “Other Procedures”.

### **2.1.3.3 Exploratory efficacy endpoint(s)**

The exploratory efficacy endpoints are:

- Time to CV death
- Time to first occurrence of Stroke (fatal and non-fatal)
- Time to first occurrence of MI (fatal and non-fatal)
- Time to all cause death
- Time to first occurrence of hospitalization for unstable angina
- Time to first occurrence of HHF
- Time to first occurrence of coronary revascularization procedures (PCI or CABG)
- Changes from Baseline to scheduled visits per protocol in:
  - HbA1c
  - Body weight
  - BP
  - UACR
  - Heart rate

### **2.1.4 Safety endpoints**

The safety endpoints include the reported adverse events (AE), hypoglycemia and other safety information, such as clinical laboratory data, vital signs, and electrocardiogram (ECG).

#### ***Observation period***

The observation period will be divided into 3 periods:

- The pre-treatment period or screening period is defined as the time from signed informed consent up to the time of first injection of the double-blind IMP
- The treatment-emergent adverse event period (on-treatment period) is defined as the time from the first injection of the IMP to the last injection of the IMP + 30 days (or +7 days for hypoglycemia).
- The posttreatment period is defined as the period after the end of the treatment-emergent adverse event period.

The on-study observation period/on-study is defined as the time from first IMP until the end of (the) study date (defined as the last scheduled visit for those who completed the study and the study discontinuation date collected on eCRF form 'Completion of End of Study' for those who did not complete the study. If death is reason collected on the 'Completion of End of Study' form, date of death will be used).

The post-study observation is defined as anything after the on-study observation period.

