The safety analysis will be conducted on the safety population that includes all randomized participants who have received at least 1 dose of double-blind treatment, regardless of the amount of treatment administered. Participants will be analyzed for safety analyses according to the treatment actually received.

All safety summaries will be descriptive; no statistical significance tests will be performed on safety data. These analyses will be based on the Safety Population. Treatment-emergent adverse events (TEAEs) are defined as AEs that developed or worsened or became serious during the period from the administration of first double-blind IMP dose treatments up to 30 days after the last administration.

Each of the two efpeglenatide treatment groups will be compared with the placebo group.

[figure not shown]
A pre-specified safety analysis will be performed in the subsets of participants on the background therapy of metformin + SGLT2, and on metformin + sulfonylurea. Safety summaries will be provided by treatment group for each of the subsets, including the summaries for AEs, SAEs, deaths, hypoglycemia, AESIs, and AEs requiring specific monitoring.

Data Monitoring Committee: Yes

See Appendix 1 ([Section 10.1](#)) for further details on Steering Committee, DMC, CEC, and Independent Expert.

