CABG: coronary artery bypass graft; ECG: electrocardiogram

Table 4 - CV Risk Factors (at least 1 criterion must be met)

-
1. Body mass index ≥ 35 kg/m² at Screening
 2. Dyslipidemia despite maximally-tolerated statin therapy:
 - Based on the last measured and documented laboratory measurement in the previous 6 months
 - LDL cholesterol >130 mg/dL (>3.36 mmol/L)
 - OR
 - HDL cholesterol <40 mg/dL (<1.03 mmol/L) for men or <50 mg/dL (<1.29 mmol/L) for women
 3. Currently smoking tobacco (Consumes an average of at least 1 cigarette, pipe, or cigar per day, at Screening)
 4. UACR ≥ 30 mg/g (3 mg/mmol) during Screening period, based on central laboratory (spot urine)
 5. SBP >140 mmHg and DBP >90 mmHg despite antihypertensive therapy at the Screening Visit
 6. Family history (in a male relative <55 years or in a female relative <65 years) of premature coronary heart disease (defined as MI or coronary revascularization procedure) in a first degree relative.
-

DBP: diastolic blood pressure; HDL: high density lipoprotein; LDL: low density lipoprotein; SBP: systolic blood pressure; UACR: urinary albumin-creatinine ratio

Sex

I 04. Male or Female

A female participant is eligible to participate if she is not pregnant (see Appendix 4 [Section 10.4]), not breastfeeding, and at least one of the following conditions applies:

- Not a WOCBP as defined in Appendix 4 (Section 10.4)

OR

- A WOCBP who agrees to follow the contraceptive guidance in Appendix 4 (Section 10.4) during the study and for at least 5 weeks after the last dose of study treatment and who agrees to refrain from donating ova for the duration of the study and at least 5 weeks after last dose of study treatment.

Informed Consent

- I 05. Capable of giving signed informed consent as described in Appendix 1 ([Section 10.1.2](#)) which includes compliance with the requirements and restrictions listed in the informed consent form (ICF) and in this protocol.

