8.2.5 Severe hypoglycemia

The definition of severe hypoglycemia is based on the American Diabetes Association workgroup on hypoglycemia classification ([17](#), [18](#)): severe hypoglycemia is an event requiring assistance of another person to actively administer carbohydrate, glucagon, or other resuscitative actions. These episodes may be associated with sufficient neuroglycopenia to induce seizure, unconsciousness or coma. Plasma glucose measurements may not be available during such an event, but neurological recovery attributable to the restoration of plasma glucose to normal is considered sufficient evidence that the event was induced by a low plasma glucose concentration. The definition of severe symptomatic hypoglycemia includes all episodes in which neurological impairment was severe enough to prevent self-treatment and which were thus thought to place participants at risk for injury to themselves or others. Note that “requiring assistance of another person” means that the participant could not help himself or herself. Assisting a participant out of kindness, when assistance is not required, should not be considered a “requiring assistance” incident.

Severe hypoglycemia will be reported as an AE. Additional information will be recorded including symptoms and/or signs, associated glucose value (if available), whether assistance was required and the treatment.

Severe hypoglycemia will be qualified as an SAE only if it fulfills SAE criteria (see Appendix 3 [[Section 10.3](#)]). For example, events of seizure, unconsciousness or coma must be reported as SAEs.

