9.4.2 Safety analyses

All safety analyses will be performed on the Safety Population.

The **observation period of safety data** is divided into 3 main segments:

- The pre-treatment period is defined as the time from informed consent up to the time of the first injection of IMP
- The on-treatment period is defined as the time from the first injection of IMP up to 30 days after the last injection of IMP
- The post-treatment period is defined as the time starting 31 days after the last injection of IMP (after the on-treatment period)

The AE observations will be classified per the observation periods of safety data as defined above into:

- **Pre-treatment AEs** are AEs that developed or worsened or became serious during the pre-treatment period
- **Treatment-emergent AEs** are AEs that developed or worsened or became serious during the on-treatment period
- **Post-treatment AEs** are AEs that developed or worsened or became serious during the post-treatment period.

The primary focus of AE reporting will be on TEAEs. Pre-treatment and post-treatment AEs will be described separately.

In addition to the on-treatment period, all AEs, SAEs, AEs leading to permanent treatment discontinuation, and AEs leading to death will be summarized for the on-study period, which is defined as the time from randomization up to the day of recorded end of study or last contact.

Table 8 - Safety analyses

Endpoint	Statistical Analysis Methods
AE	All AEs will be coded to a lowest level term (LLT), preferred term (PT), high level term (HLT), and high level group term (HLGT) and associated SOC using the version of MedDRA currently in use by the Sponsor at the time of DB lock.
SAE	
AE leading to treatment discontinuation	Adverse event incidence tables will be presented by primary SOC (sorted by internationally agreed order), HLGT, HLT and PT (sorted in alphabetical order) for each treatment group, showing the number (n) and percentage (%) of participants experiencing an AE.
AE leading to death	Adverse event incidence table will be provided by treatment group for all types of TEAEs: all TEAEs, all treatment emergent SAEs, all TEAEs leading to permanent treatment discontinuation, all TEAEs leading to death, all AESI, and AE requiring specific monitoring.
AESI	
AE requiring specific monitoring	

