## **1.6 STATISTICAL MODIFICATIONS MADE IN THE STATISTICAL ANALYSIS PLAN**

Not applicable.

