***e. Censoring for severe hypoglycemia or AE (as part of general AE analysis)***

To keep the analysis of severe hypoglycemia consistent with the overall AE analysis, for AE, a patient without an adverse event will be considered censored at the date of last IMP taken + 30 days or date of death, if earlier. For severe hypoglycemia, a patient without a severe hypoglycemia will be considered censored at the date of last IMP taken + 7 day or date of death, whichever earlier.

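### The SAP ends the on-treatment window for hypoglycemia at 7 days after the last injection, where the protocol has 30 days for all safety data, and neither explains nor records the difference

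*SAP*

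**What the plan says.** **Protocol.** Section 9.4.2 states: "The on-treatment period is defined as the time from the first injection of IMP up to 30 days after the last injection of IMP". The synopsis defines treatment-emergent AEs the same way, "up to 30 days after the last administration". Neither makes an exception for hypoglycemia. Section 8.2.5 says "Severe hypoglycemia will be reported as an AE", section 8.3 lists it among the AEs requiring specific monitoring, and Table 8 in 9.4.2 puts that category among the TEAE tables.

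**SAP.** Section 2.1.4 (Observation period) runs the treatment-emergent period to "the last injection of the IMP + 30 days (or +7 days for hypoglycemia"). Section 2.3.5.1 analyses severe hypoglycemia on that period, as number and percentage of patients and as events per 100 patient-years of IMP exposure. Appendix C item e censors patients without severe hypoglycemia at the earlier of the two dates in "date of last IMP taken + 7 day or date of death". It introduces this as a way to keep the analysis in line with the overall AE analysis, which the same item censors at 30 days.

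**Change records.** SAP Table 1 in section 1.5 lists only the on-study AE summaries and the move of the ADA endpoint. SAP 1.6, for modifications made in the SAP itself, reads "Not applicable".

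**The concern.** The protocol names severe hypoglycemia for specific monitoring. The SAP shortens the period over which its dedicated analysis counts it. An episode on day 15 after the last injection is on-treatment under the protocol, but falls outside the SAP's dedicated count, rate and censored analysis. Nothing tells the reader of the report that the window was narrowed, or why. Appendix C item e adds to the difficulty by presenting the 7-day rule as a means of consistency with a 30-day analysis.

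At stake is whether the severe hypoglycemia figures are the ones the protocol promised, and whether a reader can reconcile them with the other safety tables. No hypothesis test depends on them, since SAP 2.3.5 makes the safety analysis descriptive.

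**Working it through.** The plan gives no figure to reproduce here. The check is a comparison of texts followed by date arithmetic.

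**Step 1: windows side by side.**

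| Source | End of window for severe hypoglycemia |
|---|---|
| Protocol 9.4.2 and synopsis | last IMP + 30 days |
| SAP 2.1.4 and 2.3.5.1 | last IMP + 7 days |
| SAP Appendix C item e | last IMP + 7 days, or death if earlier |
| SAP Appendix C item e, other AEs | last IMP + 30 days, or death if earlier |

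**Step 2: days removed.** 30 − 7 = 23 days (days 8 to 30), or 23/30 = 77% of the post-dose tail. The protocol plans follow-up for 6 weeks (42 days) after the last dose, so events in these days are collected.

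**Step 3: ceiling on person-time.** With the planned 4000 participants (protocol 9.2, SAP 1.3): 4000 × 23 / 365.25 = 251.9 patient-years. This assumes that all 4000 are treated, survive and are followed through day 30, so the true figure is lower.

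**Step 4: share of the protocol's window.** For a participant treated for D years, the share is (23/365.25) / (D + 30/365.25).

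| Assumed D | Share removed |
|---|---|
| 0.25 years | 19.0% |
| 1 year | 5.8% |
| 2 years | 3.0% |
| 3 years | 2.0% |

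**Step 5: events that might move.** The documents give no severe hypoglycemia rate. At assumed rates of 0.5 to 3 per 100 patient-years, the ceiling corresponds to 0.005 × 251.9 = 1.3 up to 0.03 × 251.9 = 7.6 events over all arms.

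**Step 6: the rate's denominator.** SAP 2.3.3.1 defines exposure as last dose date minus first dose date plus 7 days. Counting events to day 30 over that exposure would put 23 days of events over no person-time, so a 30-day rate needs its own time at risk.

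**Step 7: where day 8 to 30 events can still appear.** SAP 2.3.5 and 2.3.5.1 provide on-study AE and SAE summaries, post-treatment AE and SAE tables, and a listing of severe hypoglycemia.

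**Step 8: the general TEAE tables.** SAP 2.1.4 places the 7-day exception inside the definition of the treatment-emergent period, and 2.1.4.1 classifies AEs by that definition. Read literally, a day-15 hypoglycemia is post-treatment in every table. If instead the exception is meant only for the dedicated analysis, the general tables count the event and the dedicated analysis does not. The SAP does not settle which.

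**The case against.** The best defence is that the 7 days look deliberate. They equal the weekly dosing interval, the exposure formula in SAP 2.3.3.1, and the rule in SAP 2.1.2 for classifying concomitant antidiabetic drugs. Numerator and denominator of the rate cover essentially the same time, so omitting days 8 to 30 does not by itself bias the rate. The rule is the same in every arm. All of this stands, and it is a reason to keep the 7-day result. It does not explain why the SAP leaves the protocol's window without saying so.

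Several stronger readings are tempting but unsupported:

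- **The events vanish from the report.** They do not; the outputs in step 7 remain.
- **Tables in the same report must disagree.** That is one of the two readings in step 8, not a certainty.
- **The loss is concentrated in early discontinuers.** The same 23 days come off each participant's window. Only the share of that participant's own window is larger when treatment is short.
- **The contraception period shows that hypoglycemia risk persists.** Protocol 5.1 asks women of childbearing potential to use contraception "during the study and for at least 5 weeks after the last dose of study treatment". That is a reproductive precaution and does not say how long glucose lowering or hypoglycemia risk lasts.
- **The 30-day rate would look worse.** Events and time at risk both grow, so the rate may move either way.
- **SAP 1.6 affirms that nothing changed.** Its two words show only that no modification is recorded there.

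**Conclusion.** The inconsistency is real and can be shown from the text alone. The protocol sets one 30-day window with no hypoglycemia exception; the SAP uses 7 days for hypoglycemia, without a reason or a record, and Appendix C item e misstates its own effect. The dedicated severe hypoglycemia count, rate and censored analysis therefore omit events that the protocol defines as on-treatment.

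The size is modest. The 252 patient-years is an upper bound, and the 3% share rests on an assumed 2 years of treatment. The 1.3 to 7.6 events rest on assumed rates as well as that bound. The documents do not show that the 7-day window is wrong in itself, that it favours one arm, or that it hides events from the report. This is an undocumented narrowing worth a cheap correction, with no bearing on the primary or secondary efficacy conclusions.

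**What to change.** 1. In SAP 2.3.5.1, report the number (%) with severe hypoglycemia and the event rate on the protocol's 30-day window. For the rate, use time from first dose to the earliest of last dose + 30 days, death or last contact. Show the 7-day result next to it, with the existing exposure denominator.
2. In Appendix C item e, correct the sentence that claims consistency with the overall AE analysis.
3. State that the general TEAE tables and the tables of AEs requiring specific monitoring use the 30-day window for hypoglycemia terms.
4. Record the 7-day window and the reason for it in SAP 1.6.

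The data are already collected, so the cost is SAP wording and one extra table row. The figures will differ slightly: the number (%) can only stay the same or rise, and the rate may move in either direction.
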